7.4 Laboratory Evaluations

Blood samples will be obtained for clinical laboratory evaluations on the days specified in Table 1 (Appendix A). Routine investigations will include HIV viral load, CD4 cell counts, complete blood count (CBC) with differential and measurements of hepatic (AST, ALT, ALP, GGT, bilirubin, albumin) and renal function (creatinine, GFR, urinalysis, urine albumin, Ur albumin/Cr, and Ur Protein/cr), urine and serum phosphate), calcium, glucose and lipid profiles (triglyceride, LDL, HDL, TC/HDL). These are investigations that are typically performed as part of standard of care at 3 month intervals and will not be done for study purposes but the data will be collected and recorded.

Plasma HIV RNA levels will be measured at local laboratories with a lower limit of detection as per current assays. (This [may be < 50/ml, < 40/ml or viral load not detected](#)). Clinical laboratory evaluations for hematology, biochemistry, CD4/CD8, viral load and serology will be performed at site local laboratories as per local practices.

7.5 Stored Research Samples

Blood samples will be aliquoted, frozen and stored in order to perform biomarker testing at a later date. As this field is rapidly evolving, not all tests are currently known or developed but the frozen samples will be used only for HIV research purposes and testing related to this study. The samples will not be made available to any commercial enterprise. Stored samples will be identified only by a code number and will be destroyed after 10 years.

7.6 Adherence

For self-reports of adherence will use the Visual Analogue Scale⁴⁴ (VAS last week and/or last month) which measures item ratings by participants in percentile terms from 0 to 100% and using a descriptor, for subjective perception of adherence in the last day, week, two weeks, and month. We will also collect self-reported adherence with the HIV Adherence Treatment Scale (HATS)⁴⁵. We will corroborate self-reported measure with objective outcome measurements such as returned pill counts.

7.7 Questionnaires (in Appendix)

English and Italian questionnaires

Frailty measured with some components from Frailty Phenotype

Quality of life using the EuroQoL EQ-5D⁴⁶

Fall frequency, assessed using self-administered questionnaire validated in the 2008 National Health Interview Survey Dizziness and Balance Supplement⁴⁷

7.8 Transportation of Laboratory Samples

Stored samples for biomarkers will be transported from all sites to the UHN laboratory of [name]. Details for sample shipment will be provided in the laboratory manual. All shipments will be prepared by qualified individuals ensuring that all shipments are packed and shipped according to IATA regulations for the shipment of infectious and dangerous goods.

All samples will be clearly labelled and must be accompanied with a copy of a shipment list. Prior to shipment of samples, the sites will notify the laboratory regarding the date of shipment to ensure receipt of the shipment.

8.0 STUDY VISITS

8.1 Screening visit:

The screening visit is anticipated to require 1-2 hours of the participant's time.

During this visit the following will take place:

- Informed Consent
- Assign Participant ID Number
- Demographic Information
- Medical History
- Physical Exam

- Calcium and Vitamin D intake assessment
- FRAX Score determined by country specific FRAX calculator
- Framingham Cardiovascular Risk Score
- Vital Signs including height, weight and determination of BMI
- HIV Viral load (within 1 month of screening date)
- Serum Pregnancy test and FSH (if post-menopausal)
- Hepatitis B and C (only if not previously tested)
- Hematology and biochemistry: CBC with differential and liver profile (AST, ALT, serum creatinine, Urinalysis, GFR, Urine albumin/creatinine, urine protein/creatinine) (within 1 month of screening date)
- Medication Review
- Review of Eligibility Criteria
- Dexa scan will be scheduled before baseline visit. (Dexa scan should be completed prior to Randomization.).

8.2 Baseline Visit for Participants

Day 1- Week 0 (no more than 30 days after screening visit date)

This visit must occur within 30 days of the screening visit. (**Note:** If baseline visit is within 2 weeks of screening labwork, then available screening lab results may be used and **duplicate** lab work need not be recollected). This visit is anticipated to require 2 hours of the participant's time. A baseline visit should be scheduled if the eligibility criteria met, at which the following events will take place:

- Confirmation that eligibility criteria have been met
- Confirm Dexa Scan has been completed.
- Urine Pregnancy test (if premenopausal)
- Randomization
- Targeted Physical Exam
- Vital Signs
- Framingham Cardiovascular Risk Score
- Hematology and biochemistry: CBC with differential and liver profile (AST, ALT), serum creatinine, calcium, phosphate, Urinalysis, GFR,

Urine albumin/creatinine, urine protein/creatinine, lipids- cholesterol, LDL, HDL, TG, glucose)

- CD4/CD8
- HIV Viral Load
- Research Blood Sample
- Study Drug dispensation
- Questionnaires: all questionnaires/adherence scales should be completed to include, quality of life, frailty, and falls
- Medication review
- Trabecular bone score (TBS) will be determined from the screening DXA at selected participating sites
- Participants at selected participating sites will have HRpQCT scan
- Grip strength with the dynamometer
- Tests of balance and gait - balance tests, gait speed, chair stand

8.3 Follow-up Visits for Participants

These will occur at weeks 4, 12, 24, 36, 48, 52, 60, 72, 84 and 96. At weeks 4, 12, 24, 36, 52, 60, 72, and 84, the participants will have routine investigations as per the study site, and will complete targeted physical exams. **Complete** physical exams, labwork as outlined in the schedule of Assessments on pages 25 – 26, and FSH (if premenopausal) will be required at weeks 48 and 96. Adverse events will be captured at each study visit as will any changes in clinical conditions or medications. Pill counts of returned study drug except week 52 will also be captured. The accepted windows around study visits are +/- 7 days. The procedures will last about 60 minutes.

If they agree, participants will continue to be followed even if they decide to stop the study medication

At weeks 48 and 96 all participants will complete the study imaging, collection of plasma specimens for marker banking, quality of life questionnaires, FRAX score as determined by country specific FRAX calculator, Framingham cardiovascular risk score, and geriatric measures as above. The additional procedures will last

approximately 30 minutes plus imaging time. The imaging is to be scheduled within 4 weeks of these visit dates.

Drug dispensation will be done every 3 months during the regular visits at W0, 12, W24, W36, W48, W60, W72, and 84. At week 48, all participants will receive open label TAF/FTC.

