4.0 STUDY OBJECTIVES

4.1 Primary objectives:

To determine if:

1. Switching HIV+ women on TDF/FTC to TAF/FTC increases BMD at the spine at 48 weeks relative to those who continue TDF/FTC
2. To determine if any observed improvements continue or stabilize in the year after switch.

4.2. Hypothesis generating objectives:

To determine if the effect of switching from TDF/FTC to TAF/FTC on BMD varies by stage of menopause and by third ARV.

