5.5 Secondary endpoints

We will compare changes between the immediate and delayed group from data collected at screening or baseline and weeks 48 and 96.

% change from baseline in BMD at lumbar spine at 96 weeks

% change from baseline in BMD at hip at 48 weeks

% change from baseline in BMD at hip at 96 weeks

Changes in Bone architecture as determined by Trabecular bone scan (TBS)²⁵ and HRpQCT²⁶

Changes in 10 year fracture risk determined by country specific FRAX calculator³³

% with undetectable viral load HIV-1 RNA as per current assays. (This **may be** < 50/ml, < 40/ml or viral load not detected)

Change from baseline in geriatric functional measures: frailty, performance and balance

Change from baseline in muscle quality: Sarcopenia – grip strength measured by a Dynamometer and fat free mass measure (from the DXA)

Change from baseline in lipid values and Framingham cardiovascular risk scores

Changes in renal tubular and glomerular function: eGFR, Cr, urine alb/cr and protein/cr, glucosuria

Safety (clinical and laboratory adverse events)

Changes in biomarkers of inflammation, coagulation and bone metabolism

Tolerability (EuroQoL questionnaire)

5.6 Justification of Endpoints:

Primary Endpoint: BMD assessment with dual energy x-ray absorptiometry (DXA) is well established for the diagnosis of osteoporosis and for fracture risk assessment in postmenopausal women⁷. For BMD measurements to be clinically useful, they are expressed in comparison with

established normative databases. BMD is expressed as a numerical value (g/cm²). Change in BMD is considered a valid intermediate end point for efficacy of fracture risk reduction⁷. To inform the site and timing of the primary endpoint, data from studies of bisphosphonates (a major therapy for osteoporosis) was used in which the increase in BMD is greatest at the lumbar spine, with one half of the gain of BMD achieved within 6–12 months followed by a lower increase over subsequent years³⁴

Secondary Endpoints: New imaging modalities are increasingly incorporated into studies of osteoporosis to gain more detailed information on bone strength.

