8.7 Schedule of Procedures

Study Weeks		W0	W4	W12	W24	W36	W48	W52	W60	W72	W84	W96/End of Study	W100
Study Visits	Screening (-30 days)	Baseline (screening + 30 days)											
Visit Duration	1-2 hours	2 hours	1 hour	1 hour	1 hour	1 hour	1-2 hours	1 hour	1 hour	1 hour	1 hour	1-2 hours	Phone call
Informed Consent Form	X												
Assign Subject ID number	X												
Randomization		X											
Demographics	X												
FRAX and Framingham Score	X						X					X	
Medical History	X												
Physical Exam ¹ Signs/ Symptoms	X (complete)	X	X	X	X	X	X (complete)	X	X	X	X	X (complete)	
Vital Signs including height, weight and determination of BMI	X	X	X	X	X	X	X	X	X	X	X	X	
Pregnancy test (if premenopausal), FSH	X ²	X	X	X	X	X	X ²	X	X	X	X	X ²	
HIV viral load ³	X	X ³	X ³	X	X	X	X ³	X ³	X	X	X	X ³	
CD4/CD8 count ³		X ³		X	X	X	X ³	X	X	X	X	X ³	
Hematology and biochemistry: CBC with differential and liver profile (AST, ALT, serum creatinine, calcium, phosphate, Urinalysis, GFR, Urine albumin/creatinine) ³	*X	X ³	X	X	X	X	X ³	X	X	X	X	X ³	
HBsAg, anti-HBcAb, HBsAb, HCV antibody ⁴	X ⁴												

Study Weeks		W0	W4	W12	W24	W36	W48	W52	W60	W72	W84	W96/End of Study	W100
Fasting glucose/cholesterol ³		X ³					X ³					X ³	
Research blood sample		X					X					X	
Study Drug dispensation		X		X	X	X	X	X	X	X	X	X	
Study Drug Accountability (pill counts)			X	X	X	X	X		X	X	X	X	
Questionnaires/assessments (calcium & vitamin D ⁵ , quality of life, adherence, frailty, falls, balance)	X ⁵	X					X					X	
Concomitant Medication review	X	X	X	X	X	X	X	X	X	X	X	X	
Dexa scan ⁶	X ⁶						X					X	
Trabecular bone score determined from DXA (participating sites)		X					X					X	
HRQCT scan (participating sites)		X					X					X	
Grip strength with dynamometer		X					X					X	
Test of balance and gait- balance tests, gait speed, chair stand		X					X					X	
Capture adverse events or changes in clinical conditions/medications		X	X	X	X	X	X	X	X	X	X	X	X

¹Targeted physical exam except at Screening, Weeks 48 and 96/end of study

² Serum pregnancy and FSH for all participants at screening. Urine pregnancy at all other visits, and FSH at Weeks 48 and 96/end of study **for pre-menopausal women only**

³Screening lab results may be within 1 month of screening visit. Lab collection and results as per site Standard of Care, except at Weeks 0, 48 and 96 (end of study) where lab collection and results are required. Repeat viral load and safety assessments should be done at Weeks 4 and 52.

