9.0. STUDY DRUG

Participants will take a single tablet of FTC/TDF (300/200mg) or FTC/TAF (200/**10** mg) if the third agent is a ritonavir boosted protease inhibitor, or 200mg/**25** mg if the third antiretroviral agent is an NNRTI, raltegravir or dolutegravir) ²⁴ once daily orally with the recommended dose of the co-administered third agent. For those previously on EVG/c/TDF/FTC or RPV/TDF/FTC, you will continue to receive EVG/c/TDF/FTC or RPV/TDF/FTC, or switch to EVG/c/F/TAF or RPV/F/TAF.

After 48 weeks all participants will take a single tablet of FTC/TAF (200mg/10 mg if the third agent is a ritonavir boosted protease inhibitor or 200mg/25 mg if the third agent is an NNRTI, raltegravir or dolutegravir), EVG/c/F/TAF, or RPV/F/TAF once daily.

Study drug will be donated by Gilead. Study drug will be packaged in bottles containing 30 tablets, silica gel desiccant and polyester packing material. Each bottle will be enclosed with a polypropylene screw cap. To ensure stability the drug should not be stored in any other container than that supplied. The study drug bottles will be labelled to meet all the applicable requirements of the EU guidelines to good manufacturing practice, Health Canada and the US food and drug administration. The bottles should be stored at a controlled room temperature of 25C (77F) with excursions permitted to between 15C and 30C). Storage conditions will be specified on the labels.

Until dispensed to participants, all bottles of study drug will be stored in a securely locked area, accessible only to authorized study personnel.

The third ARV agent of the participants pre-existing regimen should be taken and stored according to the approved product labeling for each particular component.

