In the GLMM model of percent change in BMD at the spine, each patient shall contribute two data points: the percent change in BMD at the spine at 48 weeks and the percent change in BMD at the spine at 96 weeks. A variogram will be used to determine the amount of error due to random effects and serial correlation. If random effects are the source of a significant amount of variation, terms for random intercept and random time shall be included in the model. If serial correlation is determined to be the main source of error, a single parameter will be required to model the correlation between the week 48 and week 96 values from a single patient, since there will be only two BMD values per patient after enrolment.

The model shall contain four covariates: (1) treatment arm, (2) a binary indicator for whether or not the data point corresponds to week 96, (3) the interaction between the treatment arm and the 96 week indicator and (4) a binary for country (Canada vs Italy). If sufficient woman are receiving hormone replacement therapy, an additional binary covariate may be included to capture whether or not the woman was receiving hormone replacement therapy at randomization.

The GLMM model can be expressed as follows:

$$Y = \beta_0 + \beta_1 \text{ treatment} + \beta_2 \text{ week 96} + \beta_3 \text{ treatment* week 96} \quad (1)$$

where Y is the percent change in BMD at the spine.

The hypothesis test for the primary analysis is $H_0: \beta_1 = 0$, which corresponds to the primary hypothesis of the effect of switching from TDF to TAF on percent change in BMD at the spine at 48 weeks.

13.3 Secondary analyses:

The secondary endpoints of greatest importance are: the percent change in BMD at the hip at week 48, the percent change in BMD at the hip at week 96, and the percentage change at the spine at week 96. GLMM will be used to estimate the effect of immediate switch to TAF/FTC on these outcomes

The hypothesis test for the secondary analysis is $H_0: \beta_3 = 0$ in model (1) above, which corresponds to the secondary hypothesis of the effect of switching from TDF to TAF on percent change in BMD at the spine at 96 weeks.

A similar model will be fit for the outcome of percent change in the spine. In that model, the hypothesis tests of $H_0: \beta_1 = 0$ and $H_0: \beta_3 = 0$ will both be of interest, corresponding to the secondary hypotheses of the effects of switching from TDF to TAF on percent change in BMD at the hip at 48 and 96 weeks, respectively.

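### The week-48 imaging window runs 4 weeks either side of the visit at which the delayed arm starts TAF/FTC, with no rule placing the scan before the first dose; the expected effect is small and a tighter window is cheap

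*Combined protocol and SAP*

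**What the plan says.** The primary objective (4.1) asks whether switching "increases BMD at the spine at 48 weeks relative to those who continue TDF/FTC". The delayed arm is the control, and its week-48 value should describe a woman still on TDF/FTC.

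Section 8.3 sets the timing of the week-48 and week-96 imaging: "The imaging is to be scheduled within 4 weeks of these visit dates". It gives no direction, so a scan before or after the visit complies. The next paragraph says "At week 48, all participants will receive open label TAF/FTC". Section 9.0 agrees: "After 48 weeks all participants will take a single tablet of FTC/TAF". The schedule in 8.7 marks both the DXA and drug dispensation at week 48 without ordering them.

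At baseline there is an order. Section 8.1 says "Dexa scan should be completed prior to Randomization", 8.2 has the site confirm that the scan is done, and footnote 6 of 8.7 repeats the rule. Week 48, the point at which half the trial changes treatment, has no counterpart.

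The model in 13.2 does not use scan date. Time enters only through "a binary indicator for whether or not the data point corresponds to week 96". Section 13.7 deals with missing values, not with mistimed ones.

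**The concern.** A delayed-arm scan taken after the week-48 visit can follow up to 4 weeks of TAF and still enter the primary analysis as a control value. The late edge of the window is the week-52 visit, by which time the delayed arm is far enough into TAF that footnote 3 of 8.7 asks for new checks: "Repeat viral load and safety assessments should be done at Weeks 4 and 52".

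The coefficient β1 is meant to compare 48 weeks of TAF with continued TDF. Late scans add some TAF effect to the control arm, but an equally late scan in the immediate arm gains the same extra weeks. If benefit accrues linearly, the two cancel. If early gain is faster than later gain, the control arm gains more and β1 moves towards no difference. Section 5.6 cites a decelerating pattern, "one half of the gain of BMD achieved within 6–12 months followed by a lower increase", but for bisphosphonates, so carrying it over to TAF is an assumption.

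Early scans matter too. They shorten the immediate arm's exposure and shrink the contrast with no contamination at all. The question is how much is lost, and to which cause.

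**Working it through.** **Inputs from the documents.** Section 13.1: difference 1%, SD 2%, 64 per arm, 80% power, significance level 0.05 (taken as two-sided). Section 8.3: imaging within 4 weeks of the visit. Section 13.7: 10% dropout before week 48.

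**Assumptions.** The documents give no time course for TAF and no distribution of scan dates. I took three shapes (linear gain, and saturating gain with a half-life of 52 or 26 weeks), scans spread evenly over the window, and the same timing in both arms.

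**The plan's own figure.** A two-sided two-sample t test with effect 1/2 = 0.5 SD needs 63.8, so 64 per arm and 128 in all. This reproduces the plan. Power at 64 per arm is 80.1%.

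**Formula.** Let g(t) be the TAF benefit after t weeks, scaled so that g(48) = 1%:

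- linear: g(t) = t/48
- half-life h: g(t) = (1 − 2^(−t/h)) / (1 − 2^(−48/h))

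For a scan u weeks from the visit, contrast = mean g(48 + u) − mean g(max(u, 0)).

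**Worked case, linear, u even over ±4.** The immediate arm averages 48/48 = 1.000. In the delayed arm, half the scans are late by 2 weeks on average, so mean exposure is 1 week and the value is 1/48 = 0.021. The contrast is 1.000 − 0.021 = 0.979.

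**Contrast in percentage points (power at 64 per arm).**

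| Scan timing | Linear | Half-life 52 | Half-life 26 |
|---|---|---|---|
| All at the visit, before the dose | 1.000 (80.1%) | 1.000 (80.1%) | 1.000 (80.1%) |
| Present rule, even over ±4 weeks | 0.979 (78.5%) | 0.972 (77.9%) | 0.964 (77.2%) |
| 4 weeks before the visit only | 0.958 (76.7%) | 0.970 (77.7%) | 0.979 (78.4%) |
| 2 weeks before the visit only | 0.979 (78.5%) | 0.985 (79.0%) | 0.990 (79.3%) |
| ±2 weeks, no order | 0.990 (79.3%) | 0.986 (79.0%) | 0.982 (78.7%) |
| All scans 4 weeks late, both arms | 1.000 (80.1%) | 0.948 (75.8%) | 0.899 (71.3%) |

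**Where the ±4-week loss comes from (percentage points).**

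| Source | Linear | Half-life 52 | Half-life 26 |
|---|---|---|---|
| Scans before the visit | 0.021 | 0.015 | 0.011 |
| Scans after the switch | 0 | 0.013 | 0.026 |

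Post-switch scans cause none of the loss under linear gain, just under half at half-life 52 (0.013 of 0.028), and most of it only at half-life 26.

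**For scale.** The expected 10% dropout leaves 64 × 0.9 = 57.6 per arm and on its own takes power to 75.8%, more than the window costs under an even spread.

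**The case against.** The strongest objection is that the missing order rule does not drive most of the number. At the present 4-week width, ordering alone gives 0.958 under linear gain and 0.970 at half-life 52, no better than the current rule. It helps only when early gain is fast. An unordered ±2-week window does about as well as the 2 weeks before the visit. This stands: width matters as much as order, and the fix has to address both.

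Second, the loss rests on assumed time courses and an assumed spread of scan dates. Sections 8.3 and 8.7 place the imaging at weeks 48 and 96, so most scans are probably meant to fall near the visit. This also stands, and it is why the result is given as a range and called small.

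Third, a tighter window could lose scans at sites with limited imaging access, which would cancel a gain of 0 to 2 power points. It would not if the window is a booking target and late scans are kept in the primary analysis.

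A reader might go further and infer that the primary comparison is seriously contaminated. If every immediate-arm scan were on time and every delayed-arm scan 4 weeks late, the contrast would fall to 0.917 (linear) or 0.860 (half-life 26), with power of 73% or 67%. The documents give no reason to expect timing to differ by arm, or all scans to fall at the late limit. Nor do they support a fear of a false positive: with equal timing and the shapes tried, the contrast never exceeds the true 1%.

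**Conclusion.** The gap is real: an in-window control value for the primary endpoint can be measured on TAF, and the analysis has no means of noticing. Its likely size is small. With scans spread evenly over ±4 weeks and equal timing in both arms, the contrast falls by 0.02 to 0.04 percentage points and power by roughly 2 to 3 points. Part of that, and all of it under linear gain, comes from early scans and not from post-switch scans.

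The conclusion rests on the assumed shapes, the even spread and equal timing by arm. Week-48 hip BMD, TBS and HRpQCT share the scheduling gap, but no size was calculated for them, and 13.3 does not plan a formal comparison of TBS. This is a minor point, worth correcting because correction is cheap and keeps control values obtained under the rule free of TAF whatever the true time course.

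**What to change.** - **Window.** In 8.3 and a footnote to 8.7, schedule week-48 imaging in both arms in the 2 weeks up to the week-48 visit and before the TAF/FTC dispensed there is started, matching the baseline rule. If that order cannot be arranged, narrow the window to ±2 weeks.
- **Which rule yields.** State that this is a booking target that does not move the switch. A scan not done by then is still done and stays in the primary analysis.
- **Data.** Record each scan date relative to the first TAF/FTC dose. Dispensing dates are already logged under 9.1.
- **Analysis.** In section 13, add a sensitivity analysis adjusting for actual scan date in both arms. Do not exclude late scans: that selects on a post-randomisation variable and loses power.

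Against an even ±4-week spread, the 2-week pre-visit window gains about 0 (linear), 1 (half-life 52) or 2 (half-life 26) power points. The cost is a short protocol amendment, which needs ethics approval at each centre (15.2), and tighter scan booking at one visit. If gain is linear and scans would otherwise fall at or after the visit, about 0.02 percentage points of contrast are given up (0.979 against 1.000).
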